9.2 Blood for ctDNA

Twenty mL of blood will be collected into EDTA tubes at the following time points:

- Prior to the start of radiation
- After the completion of radiation therapy and prior to starting chemotherapy (2-4 weeks after radiation completion)
- At the completion of chemotherapy and prior to surgery (2-4 weeks after chemotherapy completion)
- 6 months after surgery

Use BD Vacutainer purple top 10mL K₂-EDTA tubes for blood collection (Becton Dickinson catalog # 366643). Under no circumstances should blood collected in heparin tubes be used, as heparin greatly inhibits the downstream reactions. Process the blood as soon as possible after drawing (within 2 hours, upper limit 6 hours per *Parpart-Li et al, CCR, 2016*). If there is a delay between phlebotomy and processing, keep tubes in refrigerator at ~4°C. If not processed immediately, note the time delay prior to processing.

Plasma and Plasma Depleted Whole Blood (PWDB) Banking

- 1. \sim 20 ml of whole blood will be collected in K₂-EDTA tubes (purple) and placed on ice.
- 2. Pool whole blood to measure collected volume.
- 3. Split whole blood into two tubes and spin at 1800 x g for 10 minutes at $15-20^{\circ}$ C.
- 4. Remove tubes from centrifuge carefully and place on ice.
- 5. Remove supernatant (plasma) to fresh tube(s).
- 6. Spin supernatant a second time, $1800 \times g$ for 5 minutes at $15-20^{\circ}$ C.
- 7. Remove cleared plasma supernatant and aliquot into 2 ml vials. (If there is a cell pellet after 2nd spin, suspend these cells in remaining plasma and add this mixture to PDWB, see step 9).
- 8. Move frozen Plasma vials to a storage box @ -80° C.
- 9. During second plasma spin, gently mix remaining PDWB cells from step 5 above.
- 10. Remove $2 \sim 1.8$ ml PDWB aliquots, and store @ -80° C.
- 11. Ship plasma and PDWB on dry ice.

CAPP-SEq analysis will be as previously described, with barcoded adapters for library preparation, targeted DNA hybrid capture, and next-generation sequencing followed by bioinformatic correction of stereotypic errors.

All biospecimens will be marked according to individual country regulations prior to shipment to Washington University. For local specimens, take directly to the [name] lab for processing. For specimens from participating sites, ship processed specimens to the [name] lab at the address below:

10.0 DATA SUBMISSION SCHEDULE

Case report forms with appropriate source documentation will be completed according to the schedule listed in this section.

Case Report Form	Submission Schedule
Original Consent Form	Prior to registration
On-Study Form Medical History Form	Prior to starting treatment
MRgRT Treatment Summary Form	End of radiation
SOC Chemo Treatment Form	End of each cycle of SOC chemotherapy
Surgery Form Research Tissue Form	Time of surgery
Research Blood Form	Prior to starting treatment, end of radiation, end of neoadjuvant chemotherapy, 6-month follow-up
Toxicity Form	Continuous until 12 months after surgery/date of definitive end of treatment
Follow Up Form	3 months, 6 months, and 12 months after surgery
Local Control Form	12 months after start of radiation
Progression Form	Time of progression
Death Form	Time of death
MedWatch Form	See Section 8.0 for reporting requirements

Secondary sites are expected to enter data within 10 business days. Any queries generated by WUSM must be responded to within 10 days of receipt by the participating site. The WUSM research team will conduct a regular review of data status at all secondary sites, with appropriate corrective action to be requested as needed.

De-identified patient clinical data will be submitted by all non-Washington University sites on the OnCore website. No patient identifiers will be included for non-Washington University patients with the exception of dates. Unique patient identification numbers will be assigned to each patient and the corresponding patient identifiers (protected health information) will be known only to the investigators within each respective institution.

10.1 Adverse Event Collection in the Case Report Forms

All adverse events that occur beginning with start of treatment (minus exceptions defined in Section 8.0) must be captured in the Toxicity Form. Baseline AEs should be captured on the Medical History Form.

Participant death due to disease progression should be reported on the Toxicity Form as grade 5 disease progression. If death is due to an AE (e.g. cardiac disorders: cardiac arrest), report as a grade 5 event under that AE. Participant death must also be recorded on the Death Form.

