3.0 OBJECTIVES AND ENDPOINTS

Objectives	Endpoints	Justification for Endpoints
Primary		•
To quantify the pCR rate in gastric cancer patients treated with preoperative radiation	The rate of pCR (both ypT and ypN) in gastric cancer patients treated with	A complete pathologic response may result in improved oncologic
followed by total neoadjuvant chemotherapy.	preoperative radiation followed by total neoadjuvant chemotherapy.	outcomes. High rates of pCR may lead the way for future studies of non- operative management of gastric cancer.
Secondary		
To quantify the proportion of patients able to complete a full course of total neoadjuvant chemotherapy	Proportion of patients able to complete a full course of total neoadjuvant chemotherapy.	Evaluating the feasibility of total neoadjuvant therapy will help guide future trials seeking to maximize response prior to surgery.
To quantify the local control rate of gastric cancer patients treated with preoperative radiation followed by chemotherapy.	The local control rate at 1 year post RT.	Providing radiation therapy prior to chemotherapy and surgery may increase the local control rate.
To quantify the toxicity of gastric patients treated with preoperative radiation followed by chemotherapy.	The rate of grade 3 or greater toxicity as defined by CTCAE v 5.0.	Adding radiation therapy to chemotherapy and surgery may increase the toxicity associated with treatment.
To quantify the overall survival in gastric cancer patients treated with preoperative radiation followed by chemotherapy.	The overall survival at 1 year post RT.	By improving local control and pCR, overall survival may be improved.
To quantify the disease free survival in gastric cancer patients treated with preoperative radiation followed by chemotherapy.	The disease-free survival at 1 year post RT.	By improving the local control, disease free survival (locoregional and distant recurrence) may be improved as well.
Tertiary/Exploratory		
To quantify the deviation in dose to the tumor due to variation in stomach position.	Average percent difference in coverage of PTV by 95% isodose line.	The average percent difference of the five treatments represents approximately what percent of the total planned prescription was delivered to the target. Under-dosing of the tumor due to organ

[motion may regult in
		motion may result in
		decreased tumor control.
To quantify the deviation in dose	Average percentage	The average percent

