6.1 Safety Cohort and Early Stopping Rules

There will be a lead-in safety cohort of 5 patients, monitored for 30 days after completion of RT. If there is one treatment-related patient death, then the safety cohort will be expanded to 10 patients. If there are two or more treatment-related deaths, the radiation dose will be decreased to 20 Gy in 5 fractions. The trial will be terminated if there are more than three treatment-related deaths (equaling approximately 10% of the entire projected accrual).

Treatment-related grade 5 toxicities should be reported to the institutional PI within 24 hours and to the WUSM PI according to the timelines in Section 8.2.

For the purposes of the early stopping rules, "treatment-related" refers to both adaptive SCRT and SOC total neoadjuvant chemotherapy.

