7.0 DOSE DELAYS/DOSE MODIFICATIONS

7.1 **Dosing Adjustments for Radiation Therapy**

Radiotherapy for this trial may take place over a maximum of 10 business days before it is considered a protocol deviation. There are no dose adjustments (reductions, omissions) associated with radiotherapy.

7.2 **Dosing Adjustments for Chemotherapy**

Dose reductions and holds for chemotherapy may be made at the discretion of the treating physician. All chemotherapy is being given as per standard of care, and dosing is not dictated by this protocol. Please refer to the package insert of each drug for recommended dosing adjustments.

8.0 **REGULATORY AND REPORTING REQUIREMENTS**

The entities providing oversight of safety and compliance with the protocol require reporting as outlined below. Please refer to Appendix B for definitions and Appendix C for a grid of reporting timelines. All investigators treating patients on this study are responsible for ensuring that serious adverse events (as defined in Appendix B) are reported to the WUSM PI within an adequate timeframe for the event to be assessed by the WUSM PI for reporting to HRPO and QASMC.

Adverse events will be tracked from baseline through 12 months after surgery (or, for patients who do not undergo surgery, 12 months after definitive end of treatment). All adverse events must be recorded on the toxicity tracking case report form (CRF) with the exception of:

• Baseline adverse events, which shall be recorded on the medical history CRF

• Adverse events that are thought to be at least possibly related to a non-protocol treatment received after the patient comes off SCRT or neoadjuvant chemotherapy

Refer to the data submission schedule in Section 11 for instructions on the collection of AEs in the EDC.

Reporting requirements for Washington University School of Medicine study team may be found in Section 8.1. Reporting requirements for secondary site study teams participating in WUSM-coordinated research may be found in Section 8.2.

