14.3 Analysis of Secondary Endpoints

Secondary endpoints include the following:

- The proportion of patients that can complete total neoadjuvant chemotherapy.
- The local control rate at 1 year will be described as percent with 95% confidence interval. Local control is defined as no local recurrence, calculated from RT start.
- The rate of grade 3 or higher toxicity will also be described as percent with 95% confidence interval.
- Kaplan-Meier estimates will be used to describe disease-free survival (no cancer evident or death) and overall survival (survival from start of RT) at 1 year.

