APPENDIX C: Reporting Timelines

Expedited Reporting Timelines				
Event	HRPO	QASMC		
Unanticipated problem	Report within 10 working days. If the	Report via email after IRB		
involving risk to participants or	event results in the death of a participant	acknowledgment		
others	enrolled at WU/BJH/SLCH, report			
	within 1 working day.			
Major deviation	Report within 10 working days. If the			
	event results in the death of a participant			
	enrolled at WU/BJH/SLCH, report			
A series of minor deviations	within 1 working day.			
that are being reported as a	Report within 10 working days.			
continuing noncompliance				
Protocol exception	Approval must be obtained prior to			
1 lotocol exception	implementing the change			
Complaints	If the complaint reveals an unanticipated			
	problem involving risks to participants			
	or others OR noncompliance, report			
	within 10 working days. If the event			
	results in the death of a participant			
	enrolled at WU/BJH/SLCH, report			
	within 1 working day. Otherwise, report			
	at the time of continuing review.			
Breach of confidentiality	Within 10 working days.			
Incarceration	If withdrawing the participant poses a			
	safety issue, report within 10 working			
	days.			
	If with drawing the norticing at damaged			
	If withdrawing the participant does not			
	represent a safety issue and the patient will be withdrawn, report at continuing			
	review.			
	10110111			

	Routine Reporting Timelines					
Event	HRPO	QASMC				
Adverse event or SAE that does not require expedited reporting	If they do not meet the definition of an unanticipated problem involving risks to participants or others, report summary information at the time of continuing review	Adverse events will be reported in the toxicity table in the DSM report which is typically due every 6 months.				
Minor deviation	Report summary information at the time of continuing review.					
Complaints	If the complaint reveals an unanticipated problem involving risks to participants or others OR noncompliance, report within 10 working days. If the event results in the death of a participant enrolled at WU/BJH/SLCH, report within 1					

Routine Reporting Timelines					
Event	Event HRPO				
	working day. Otherwise, report at the time of				
	continuing review.				
Incarceration	Incarceration If withdrawing the participant poses a safety issue, report within 10 working days.				

Expedited Reporting Timelines for Secondary Sites				
Event	Local IRB			

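### Does entering progression deaths on the Toxicity Form as grade 5 mean they count in the grade 3+ toxicity rate?

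*Combined protocol and SAP*

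**What the plan says.** Section 10.1 gives two instructions for deaths. For cancer deaths, "Participant death due to disease progression should be reported on the Toxicity Form as grade 5 disease progression". For other deaths, "If death is due to an AE (e.g. cardiac disorders: cardiac arrest), report as a grade 5 event under that AE". Every death also goes on the Death Form.

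The endpoint is set in 3.0 as grade 3 or greater toxicity by CTCAE v5.0, with the reason that "Adding radiation therapy to chemotherapy and surgery may increase the toxicity associated with treatment". The analysis in 14.3 is one line: "The rate of grade 3 or higher toxicity will also be described as percent with 95% confidence interval". Section 6.6 fixes the denominator as patients given at least one radiation fraction. None of these sections limits the numerator by attribution or by term.

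Elsewhere the word toxicity is used broadly. Section 8.0 says "All adverse events must be recorded on the toxicity tracking case report form (CRF) with the exception of" two classes: baseline events, and events possibly related to later non-protocol treatment. Appendix C adds: "Adverse events will be reported in the toxicity table in the DSM report which is typically due every 6 months". Section 8.4 exempts progression-related events from expedited reporting only. Section 6.1 says that treatment-related "refers to both adaptive SCRT and SOC total neoadjuvant chemotherapy", but only for the early stopping rules.

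**The concern.** Taken together, these sections seem to put cancer deaths into a safety rate. The form is called a toxicity form, the death is entered at grade 5, the endpoint takes grade 3 and above, and no sentence removes the progression term. The exceptions in 8.0 and 8.4 do not remove it, and the definition in 6.1 does not reach this endpoint.

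At stake would be the reproducibility and labelling of a published safety figure. Two analysts could report different rates, and one could show grade 5 toxicity in a trial with no toxic death. The 1-year survival estimate would not pick up all the same deaths, because the form can stay open longer than the horizon for "overall survival (survival from start of RT) at 1 year".

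**Working it through.** **Reading the sections side by side**

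1. Section 10.1 says which form and grade to use. Section 14.3 says what is estimated. No text joins them by defining the rate as the share of patients with any grade 3+ row.
2. Within 10.1, progression death is one case and death due to an adverse event is the other. The progression case is thus handled as something other than an adverse event, although it sits on the same form.
3. The reason given in 3.0 is added harm from treatment, and a death from gastric cancer is not that.
4. If the rate is read as treatment-related, these deaths drop out. If it is read as all adverse events whatever the cause, they still drop out provided the distinction in 10.1 is kept. They enter only if row counting is assumed.
5. They can be identified from their own term on the Toxicity Form and from the Death Form. Appendix E also gives monitors a cause-of-death column.

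**Size if they were counted**

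Inputs: N = 36 (14.1); denominator of patients with at least one fraction (6.6), so at most 36. The documents give no toxicity rate and no progression-death rate.

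The plan's only precision figure is for pathologic complete response: 20% of 36, with an interval of 9% to 37%. The exact (Clopper-Pearson) interval at 7.2/36 is 8.6% to 36.7%, which reproduces it. The same method is used below.

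- One progression death in a patient with no other grade 3+ event: 1/36 = 2.8 points. Two: 2/36 = 5.6 points. If only 30 were evaluable (an assumption): 1/30 = 3.3 points.
- A death in a patient already counted as grade 3+: 0 points.
- Illustration with 11 patients having genuine grade 3+ toxicity (assumed): 11/36 = 30.6% (16.3% to 48.1%). One added death: 12/36 = 33.3% (18.6% to 51.0%). Two: 13/36 = 36.1% (20.8% to 53.8%).
- At 18/36 the interval is 32.9% to 67.1%, so one or two deaths move the rate by much less than its sampling error.

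A wider range needs assumed rates. Let t be the true grade 3+ rate, q the proportion with progression death while the form is open, and take the two as independent. Patients added = 36 × q × (1 − t). With t = 50% and q = 5%: 36 × 0.05 × 0.5 = 0.9 patients, or 2.5 points. With t = 20% and q = 20%: 36 × 0.20 × 0.8 = 5.8 patients, or 16 points. None of these rates is in the documents.

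**Form window against 1-year survival**

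For an operated patient at the shortest intervals (Sections 1.0 and 10.0): radiation 0.16 months + 2 weeks (0.46) + chemotherapy + 2 weeks (0.46) + 12 = 13.1 months plus the length of chemotherapy. With a full 4 months before surgery this is 17.1 months from the start of radiation. That is not a firm lower bound, because 6.9 says up to 4 months, and 6.0 and 6.3 let patients finish chemotherapy after surgery. There is no firm upper bound either, because 6.3 allows longer delays after discussion with the Principal Investigator. The form does outlast the 1-year horizon for operated patients, by an amount that varies.

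**The case for a change.** The strongest case for a change is that probable intent is not a rule. The protocol calls the adverse event form and the adverse event table toxicity documents, Appendix B defines an adverse event regardless of relatedness, and no sentence excludes the progression term. Settling the point before results are known would remove a choice made after the fact, at the price of one sentence. Under the least favourable assumptions above, the shift of 16 points is no longer small beside the sampling error.

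Part of this stands. There is no explicit exclusion, and the plan does not say whether the rate is all-cause or treatment-related. Non-fatal grade 3+ events caused by progression have no separate field in the documents, so the ease of filtering is shown only for deaths.

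The rest is weaker. The 16-point figure needs assumed rates and also an analyst who treats rows labelled disease progression as toxicity, against 10.1 and 3.0. A row with that label would not readily pass for a toxic death, and the plan sets no separate grade 5 endpoint. The mismatch with 1-year survival does not bear on whether these deaths are toxicity.

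**Conclusion.** The gap in wording is real, but it is one that an analyst fills sensibly from the protocol itself: progression deaths are left out of the toxicity numerator and shown separately. The structure of 10.1 and the rationale in 3.0 both point that way, and the data collected for these deaths allow it.

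If they were counted anyway, the effect would be 2.8 points per non-overlapping death with 36 evaluable patients, and zero for overlapping ones. The total cannot be derived from the documents. The rate is a descriptive secondary estimate with no test, threshold or decision attached. The primary endpoint does not use it, the stopping rule counts only treatment-related deaths, and monitors see cause of death by patient.

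This conclusion rests on the site's assignment of cause of death, which 10.1 already requires, and on the analyst following the distinction drawn there. It does not settle the broader all-cause or treatment-related reading for non-fatal events. No change to the plan is called for on this point.

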11.0 MEASUREMENT OF EFFECT

Effect will be measured by the rate of pCR (primary and nodal) found at the time of surgical resection. Partial pathologic response will be defined as < 10% viable tumor remaining. Residual disease will be documented in the form of % treatment response and % viable tumor. No radiographic response to treatment will be recorded or assessed.

12.0 DATA AND SAFETY MONITORING

In compliance with the Washington University Institutional Data and Safety Monitoring Plan, an independent Data and Safety Monitoring Board (DSMB) will be specifically convened for this trial to review toxicity data. The DSMB will consist of no fewer than 3 members including 2 clinical investigators and a biostatistician. DSMB members must be employed by Washington University, Barnes-Jewish Hospital, or St. Louis Children's Hospital (unless an external ad hoc member is necessary due to a conflict of interest). Like investigators, DSMB members are subject to the Washington University School of Medicine policies regarding standards of conduct. Individuals invited to serve on the DSMB will disclose any potential conflicts of interest to the trial principal investigator and/or appropriate university officials, in accordance with institution policies. Potential conflicts that develop during a trial or a member's tenure on a DSMB must also be disclosed.

Until such a time as the first secondary site enrolls its first patient, a semi-annual DSM report to be prepared by the study team will be submitted directly to the Quality Assurance and Safety Monitoring Committee (QASMC) (bypassing the independent DSMB). The first report is required either 30 days after the enrollment of the 5th participant (if sooner than 6 months after study activation) or 6 months after study activation (provided at least one patient has been enrolled; if zero patients have been enrolled at the 6-month mark, the first report will be required one year after accrual opens provided at least one patient has been enrolled).

The DSM report for the DSMB will be prepared by the study team with assistance from the study statistician. Following review by the DSMB, the report and the DSMB's recommendations will be submitted to the QASM Committee. The DSMB must review this study at least every six months

beginning six months after enrollment of the first patient at a secondary site, no more than one month prior to the due date of the DSM report to QASMC. This report will include:

- Study demographic information (local protocol number, protocol title, list of primary study team members, study sites, primary and secondary sponsors, date of most recent QA audit, and study status and history (including activation and suspension dates)
- Accrual information, including study-wide target accrual and actual accrual, anticipated and/or actual accrual end date, and accrual by year by site
- Subject status information presented in both cumulative format (total number of subjects who consented, enrolled, screen failed, started intervention, discontinued intervention, went off study, expired) and current format (number of subjects in screening, on intervention, in follow-up, or off study at time of report)
- Protocol objectives and the number of participants who are evaluable for each objective
- History of study (including summaries of substantive amendments, accrual suspensions and reasons, protocol exceptions, errors, and breaches of confidentiality)
- Summary of exceptions, noncompliance reports, and unanticipated problems reported to the IRB
- Early stopping rules and data describing whether the stopping rules have been met
- Separate SAE and worst grade toxicity tables, each separated by site
- Participant-level response and survival data
- Summary of specimen collection (percentage of participants who have had specimens collected at each required time point)
- Abstract submissions/publications
- Summary of any recent literature that may affect the safety of participants or the ethics of the study

Further DSMB responsibilities are described in the DSMC charter.

The study principal investigator and coordinator will monitor for serious toxicities on an ongoing basis. Once the principal investigator or coordinator becomes aware of an adverse event, the AE will be reported to the HRPO and QASMC according to institutional guidelines (please refer to Section 8.0).

Refer to the Quality Assurance and Safety Monitoring Committee Policies and Procedures and the Siteman Cancer Center Independent Data Safety Monitoring Board (DSMB) Policies and Procedures documents for full details on the responsibilities of the DSMB. This is located on the QASMC website at https://siteman.wustl.edu/research/resources-for-researchers/quality-assurance-and-safety-monitoring/.

